#### 9.4. Data Sources

### 9.4.1. HIRD, US

The HIRD is a longitudinally integrated research database comprising automated payment claims for healthcare encounters since 01 January 2006 from included health insurance plans across the US. It is among the largest of its kind in the US, with current enrollment of approximately 70 million members as of 2018. The HIRD has been extensively used for pharmacoepidemiologic research, including many post approval safety studies. The HIRD includes enrollment data, medical care, physician specialty, laboratory results (one third of patients), prescription drug use, and healthcare utilization that can be tracked for each individual throughout the course of their enrollment.

#### PFIZER CONFIDENTIAL

CT24-WI-GL02-RF023.0 Non-Interventional Study Protocol Template For Secondary Data Collection Study 20-May-2021

Page 34

### 9.4.2. Swedish Registers, Sweden

The Swedish registry data include five large, nationally held registers: the Swedish NPR, the Swedish Prescribed Drug Register (SPDR), the Swedish Cancer Register (SCR), the Cause of Death Registry, and the Total Population Register (TPR). These registers include data for patients, drugs, cancer, death, and the population linkable by patients' personal identity numbers. Entrance into the registers is upon birth or immigration to Sweden and exit from the registers is upon death or emigration.

Healthcare in Sweden is primarily government-funded and managed at the national, regional, and local level. Only a small proportion of the population (6%) also have some type of supplementary private health insurance. In most regions, there is no formal gatekeeping and patients may contact specialists directly. Applications for data access are sent to the National Board of Health and Welfare and Statistics Sweden and processed by a pre-defined data permit process. The data permit process is preceded by a separate ethical review process by the Swedish Ethical Review Agency. The five Swedish registers are detailed below.

- The Swedish NPR includes information regarding inpatient and outpatient non-primary (i.e., specialist) encounters across Sweden; outpatient general practice encounters are not captured in the NPR. Beginning in 1987, coverage for inpatient admissions became nationwide and is near 100%. Coverage for outpatient non-primary care began nationwide in 2001 and is around 87% (although it may be higher for somatic care such as rheumatology). Key variables include diagnosis, surgery, external causes of injury (E codes), age, sex, hometown, hospital, specialty, and information related to hospital admissions and discharges (e.g., dates, main and contributory diagnoses, mode of discharge). Information on patient anthropometric data (e.g., height, weight, body mass index [BMI]) is not available nor are laboratory test results (e.g., absolute lymphocyte count, blood lipid levels) or clinical measurements (e.g., blood pressure). A number of diagnoses have been reported to have high positive predictive values in the inpatient register. The NPR is updated annually.
- The SPDR, maintained by the National Board of Health and Welfare, contains information on all prescribed and dispensed medication for patients in Sweden. The SPDR was started in July 2005. The register contains data recorded using personal identification numbers and can thus be linked with other Swedish registers. Coverage of prescriptions is close to 100%, however, inpatient administrations and hospital administered drugs in specialized outpatient care are not captured. Information recorded in the SPDR includes basic demographic characteristics such as age, sex, and residency, as well as medication-specific information such as the prescribed/dispensed drug (e.g., ATC code, International Non-proprietary Names), prescription dispensing date, pack size, dispensed amount, formulation, dosage, prescribing healthcare practitioner, and costs. The SPDR is updated monthly.
- The Swedish Cancer Register was started in 1958 and is managed by the National Board of Health and Welfare. The registry records every cancer case diagnosed by clinical, morphological or other laboratory examinations as well as cases diagnosed at autopsy. Since the mid-1980s there are six regional registries associated with the oncological centers in each medical region of Sweden where the registration, coding and major check-up and

#### PFIZER CONFIDENTIAL

correction work is performed. The register includes information on patient characteristics, tumor characteristics, diagnosis, and date and cause of death. Data is updated on an annual basis with a lag time of approximately 13 months.

- The Swedish Cause of Death Registry has been maintained by the National Board of Health and Welfare since 1994 and uses the International Classification of Diseases (ICD) coding, but the rules of the World Health Organization. Variables include, date of birth, country of birth, nationality, sex, marital status, date of death, underlying cause of death, and contributing causes of death. Data are updated annually.
- Patient demographics are available from the national TPR, maintained by Statistics Sweden since 1968. The TPR is produced by the Swedish Tax Agency and the data are transferred to Statistics Sweden. The TPR covers all registered individuals in Sweden and their personal identity numbers with 100% coverage. The register includes demographic information related to population size and composition, such as age, sex, marital status, nationality, place of birth, place of residency in Sweden, migrations within Sweden and to/from abroad, births and deaths. The TPR will be used to ascertain length of medical history available for women eligible for the study (i.e., an enrollment file).

Unless specified otherwise, the Swedish registries are updated yearly, and it can take six to nine months to receive a data extraction. As a result, there is a lag in data availability of approximately 12-18 months.

# 9.5. Study Size

# 9.5.1. HIRD, US

For the purposes of calculating sample size, the study is designed to have sufficient size to detect a risk of endometrial cancer for women using LDVE that is 1.5 times the risk of endometrial cancer associated with no use of LDVE. For the HIRD, assuming a 1:4 exposed:comparator ratio,  $\alpha$ =0.05, a median follow-up duration of 2.4 years, and a background endometrial cancer incidence rate of 74.5 events per 100,000 person-years, the study would require 33,377 LDVE users and 133,504 non-users to achieve 80% power to detect a hazard ratio of 1.5. To detect a hazard ratio of 1.5, the number of endometrial cancer events required is 60 events in the exposed and 239 events in the comparator. Based on a median duration of 2.4 years, the total number of person-years needed to observe the required number of events is 80,105 person-years in the LDVE cohort and 320,410 person-years in the non-user cohort.

Preliminary patient counts for the study period in the HIRD show that the cohort of LDVE new users (exposed) in the primary analysis will include approximately 152,941 women. Based on a 1:4 exposed:comparator ratio, the potential non-users comparator cohort in the primary analysis will include 611,764 women. Given the available sample sizes, the study will have >99% power to detect a hazard ratio of 1.5 for the LDVE new users cohort.

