The Swedish registry data includes five, large, nationally held registers: the Swedish National Patient Register (NPR), the Swedish Prescribed Drug Register (SPDR), the Swedish Cancer Register (SCR), the Cause of Death Registry, and the Total Population Register (TPR). These registers include data for patients, drugs, cancer, death, and the population linkable by patients' personal identity numbers. Entrance into the registers is upon birth or immigration to Sweden and exit from the registers is upon death or emigration.

**Study Size:** The study is designed to have sufficient size to detect with 80% power the hazard of endometrial cancer for women using unopposed LDVE that is 1.5 times the hazard of endometrial cancer associated with no use of vaginal estrogen. In the HIRD, assuming a 1:4 exposed:comparator ratio,  $\alpha$ =0.05, a median follow-up duration of 2.4 years, and a background endometrial cancer incidence rate of 74.5 events per 100,000 person-years, the study would require 33,377 LDVE users and 133,504 non-users to achieve 80% power to detect a hazard ratio of 1.5. For the comparison between LDVE new users and non-users in the primary analysis, the sample is estimated to include at least 152,941 new users and 611,764 non-users. Given the available sample sizes, the study will have >99% power to detect a hazard ratio (HR) of 1.5 for the LDVE new users cohort.

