#### 9.5.2. Swedish Registers, Sweden

Any data extraction from the Swedish national registries requires a full data application, with an estimated timeline of six to nine months. Thus, applying for raw data for the purpose of estimating study size was not feasible due to the strict timelines of this protocol. Therefore, the size of the Swedish study population was estimated based on officially available information.

The publicly available data does not allow to accurately consider the interactions between the various exclusion criteria of this study. When estimating the study size, several assumptions were made to compensate for this, which should be kept in mind when interpreting the resulting estimates. For details about the assumptions used to estimate study size in Sweden, see Annex 3.

In Sweden, the LDVE new users cohort is estimated to include 100,800 women. The non-users cohort is estimated to include 1,378,928 women.

Assuming a 1:4 exposed:comparator matching ratio,  $\alpha$ =0.05, a median duration of follow-up of 2.4 years, and a background endometrial cancer incidence rate of 70.4 events per 100,000 person-years, the study would have >99% power to detect a hazard ratio equal to 1.5 for the new users of LDVE cohort. For achieving a power of 80% to detect a hazard ratio of 1.5, the total number of endometrial cancer events required is 299. The total number of person-years needed to observe the required number of events is 84,770 person-years in the LDVE new users cohort and 339,077 person-years in the non-users cohort. Equivalently, the sample size (after matching) required for achieving 80% power is 35,321 in the LDVE new users cohort and 141,282 in the non-users cohort.

Additional details about the estimated study population size are described in Annex 3.

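### The 299-event total is right for a hazard ratio of 1.5, but the per-arm split, person-years and cohort sizes use one rate for both arms and overstate the 80%-power requirement by about 10%

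*Protocol*

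**What the plan says.** Protocol section 9.5.1 (HIRD) takes an LDVE risk 1.5 times that without LDVE as the effect to detect. Its assumptions are "For the HIRD, assuming a 1:4 exposed:comparator ratio", alpha 0.05 with no sidedness given, and "a median follow-up duration of 2.4 years, and a background endometrial cancer incidence rate of 74.5 events per 100,000 person-years". It concludes that "the study would require 33,377 LDVE users and 133,504 non-users to achieve 80% power to detect a hazard ratio of 1.5" and that "the number of endometrial cancer events required is 60 events in the exposed and 239 events in the comparator". The person-years needed are given as "80,105 person-years in the LDVE cohort and 320,410 person-years in the non-user cohort".

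Section 9.5.2 (Sweden) uses the same HR, ratio, alpha and 2.4 years with a background rate of 70.4 per 100,000 person-years. It gives a total of 299 events, "84,770 person-years in the LDVE new users cohort and 339,077 person-years in the non-users cohort", and 35,321 and 141,282 women. It does not give events by arm.

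The Study Size paragraphs of the abstract (section 4) repeat the HIRD cohort sizes and the Swedish total, person-years and cohort sizes. The 60/239 split appears only in section 9.5.1.

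Both sections also claim more than 99% power with the cohorts expected to be available: 152,941 LDVE new users in the HIRD and 100,800 in Sweden.

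**The concern.** Dividing the stated events by the stated person-years gives almost the same rate in each arm. Figures offered as the requirement for detecting an HR of 1.5 therefore describe two arms with no difference in incidence. With 1:4 person-time and an HR of 1.5, events should fall in the ratio 1.5:4, not 1:4.

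At stake is the accuracy of the numbers that the protocol attaches to 80% power. A reader who compared observed counts with 60 and 239 would be comparing them with what no effect looks like. Anyone who redid the calculation by the same route for a different ratio or cohort would repeat the error.

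**Working it through.** **Inputs** (sections 9.5.1 and 9.5.2): HR 1.5; power 80%; alpha 0.05, taken as two-sided because that reproduces the plan's total (one-sided gives 236 events); exposed share 0.2; 2.4 years per woman; background rate 74.5 (HIRD) and 70.4 (Sweden) per 100,000 person-years.

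**1. Reproduce the total.** Schoenfeld: D = (1.96 + 0.8416)² / (0.2 × 0.8 × (ln 1.5)²) = 298.4, rounded up to 299. This agrees with the plan.

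**2. Reproduce the plan's other figures.** Split 298.39 by allocation: 0.2 × 298.39 = 59.68 and 0.8 × 298.39 = 238.71, which are the stated 60 and 239. Divide both by the same background rate, then by 2.4 years.

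- HIRD exposed: 59.68 / 0.000745 ≈ 80,105 person-years; / 2.4 ≈ 33,377 women.
- HIRD comparator: 238.71 / 0.000745 ≈ 320,416 person-years (stated 320,410, a rounding difference); 320,410 / 2.4 ≈ 133,504 women.
- Sweden: 59.68 / 0.000704 and 238.71 / 0.000704 give the stated 84,770 and 339,077 to within rounding; / 2.4 gives 35,321 and 141,282 women.

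One recipe therefore yields every stated figure. One-sided Schoenfeld, Freedman, Wald rate-ratio and two-proportion calculations do not give the HIRD figures.

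**3. Rates implied by the stated figures.** HIRD: 60 / 80,105 = 74.9 and 239 / 320,410 = 74.6 per 100,000, a ratio of 1.0 apart from rounding. Sweden: 84,770 × 0.000704 = 59.7 and 339,077 × 0.000704 = 238.7, so the person-years reach the total only if both arms carry the background rate.

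**4. What the stated person-years deliver at HR 1.5.** HIRD exposed: 80,105 × 0.000745 × 1.5 = 89.5; comparator: 320,410 × 0.000745 = 238.7; total about 328. Sweden also gives about 328. Power = Φ(√(328.2 × 0.16) × ln 1.5 − 1.96) = 0.836.

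**5. Requirement with the exposed rate at 1.5 × background.** With 1:4 person-time, D = P × r × (1.5 + 4), where P is the exposed person-years and r the background rate, so P = D / (5.5 r). The ranges below run from D = 298.4, which the plan's person-years use, to D = 299.

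| | Stated | Recomputed |
|---|---|---|
| HIRD events, exposed / comparator | 60 / 239 | about 82 / 217 |
| HIRD person-years, exposed | 80,105 | 72,800-73,000 |
| HIRD person-years, comparator | 320,410 | 291,300-291,900 |
| HIRD women, exposed | 33,377 | 30,300-30,400 |
| HIRD women, comparator | 133,504 | 121,400-121,600 |
| Sweden person-years, exposed | 84,770 | 77,100-77,200 |
| Sweden person-years, comparator | 339,077 | 308,300-308,900 |
| Sweden women, exposed | 35,321 | 32,100-32,200 |
| Sweden women, comparator | 141,282 | 128,400-128,700 |

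The split is 299 × 1.5/5.5 = 81.5 and 299 × 4/5.5 = 217.5. Size of the overstatement in the HIRD: 80,105 / 72,971 = 1.098 with 299 events and 80,105 / 72,822 = 1.100 with 298.4. Sweden is the same.

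**6. Check the >99% claims.** Expected events at HR 1.5 with 1:4 matching: HIRD 152,941 × 2.4 × 0.000745 × 5.5 ≈ 1,504, power above 99.9%; Sweden 100,800 × 2.4 × 0.000704 × 5.5 ≈ 937, power about 99.9%. Both claims hold.

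**The case against.** The best defence is that the rate is a population figure meant for the whole cohort. Total person-years would then be right: (80,105 + 320,410) × 0.000745 = 298.4 and (84,770 + 339,077) × 0.000704 = 298.4, and the stated sizes would give 80% power. The HIRD rate is referenced to a study of endometrial cancer trends in US women of menopausal age, and the Swedish rate to a cancer statistics database, so the reading is possible. It is strained, because the protocol calls the rate background and sets it beside a contrast with no use of vaginal estrogen. It also does not rescue the 60/239 split, which implies an HR of 1.0 whatever the rate means.

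A second objection is that Schoenfeld's formula itself uses the allocation proportions. It does, in the variance behind the total, and that total is accepted here. This does not justify applying the unexposed rate to the exposed arm when converting events to person-years.

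A third is that the replacement figures depend on the method. This stands. The protocol names no formula, and Wald or two-proportion calculations would put the HIRD exposed requirement between 24,476 and 27,363 women. The recomputed values are therefore approximate and conditional on Schoenfeld, the method that reproduces the plan's own figures.

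A reader might also infer that 33,377 or 35,321 serves as a benchmark if matching yields fewer women. No section uses them so: section 9.7.1 lowers the matching ratio without reference to these sizes.

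**Conclusion.** The point holds as an arithmetic inconsistency of minor consequence. Section 9.5.1 splits a correct total by allocation ratio, and the person-years and cohort sizes in sections 9.5.1, 9.5.2 and the abstract apply the background rate to both arms. That implies an HR of 1.0 and overstates the requirement for 80% power by about 10%; at HR 1.5 the stated sizes give about 84%.

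Two stronger readings are tempting and are not supported. A reader might infer that the event requirement itself assumes no effect; it does not, since 299 depends on HR 1.5 and is right. A reader might infer that the study's power is in doubt. The error runs the other way, and the available exposed cohorts are about 4.6 times (152,941 / 33,377) and 2.9 times (100,800 / 35,321) the stated need.

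The conclusion assumes two-sided alpha, Schoenfeld's formula and a background rate that is the non-user rate. Without the last assumption only the 60/239 split remains wrong.

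**What to change.** Keep 299 events. In section 9.5.1, restate the split as about 82 exposed and 217 comparator events. In sections 9.5.1, 9.5.2 and the abstract, replace the person-years and cohort sizes with the recomputed values above, given as approximate, and state that they rest on two-sided Schoenfeld and on the background rate being the rate in non-users. Alternatively, keep the stated person-years and sizes, correct the HIRD events expected at HR 1.5 to about 90 and 239, and state about 84% power instead of 80%.

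Either way the cost is a text correction. The cohorts, matching, analyses, timelines and >99% power statements are unchanged.

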#### 9.5.2. Swedish Registers, Sweden

Any data extraction from the Swedish national registries requires a full data application, with an estimated timeline of six to nine months. Thus, applying for raw data for the purpose of estimating study size was not feasible due to the strict timelines of this protocol. Therefore, the size of the Swedish study population was estimated based on officially available information.

The publicly available data does not allow to accurately consider the interactions between the various exclusion criteria of this study. When estimating the study size, several assumptions were made to compensate for this, which should be kept in mind when interpreting the resulting estimates. For details about the assumptions used to estimate study size in Sweden, see Annex 3.

In Sweden, the LDVE new users cohort is estimated to include 100,800 women. The non-users cohort is estimated to include 1,378,928 women.

Assuming a 1:4 exposed:comparator matching ratio,  $\alpha$ =0.05, a median duration of follow-up of 2.4 years, and a background endometrial cancer incidence rate of 70.4 events per 100,000 person-years, the study would have >99% power to detect a hazard ratio equal to 1.5 for the new users of LDVE cohort. For achieving a power of 80% to detect a hazard ratio of 1.5, the total number of endometrial cancer events required is 299. The total number of person-years needed to observe the required number of events is 84,770 person-years in the LDVE new users cohort and 339,077 person-years in the non-users cohort. Equivalently, the sample size (after matching) required for achieving 80% power is 35,321 in the LDVE new users cohort and 141,282 in the non-users cohort.

Additional details about the estimated study population size are described in Annex 3.

#### 9.6. Data Management

#### 9.6.1. HIRD, US

All analyses will be conducted using Statistical Analysis System ([SAS®]; SAS Institute Inc., Cary, North Carolina, US) software version 9.2 or higher and R version 3.0 or higher.

#### 9.6.2. Swedish Registers, Sweden

In Sweden, raw data are stored at the different National Registers and linkage is performed centrally by government agencies (the National Board of Health and Welfare and Statistics Sweden). Due to legislation prohibiting Swedish patient-level data from leaving the country, the linked and deidentified dataset will be provided to IQVIA in Sweden. The IQVIA investigators in Sweden will use SAS® software or other appropriate analytical software to access the raw data, manage the analytic datasets, and conduct data analysis locally. This study will follow the relevant chapters of the European Network of Centres for Pharmacoepidemiology and Pharmacovigilance (ENCePP) and the International Conference on Harmonisation guidelines for data management. In addition, the data will be checked for consistency in terms of the range of values, units of measurement, and relevance of clinical information (e.g., a prostate cancer diagnosis for a female patient).

#### 9.6.3. Case Report Forms (CRFs)/Electronic data record

As referred to in the Validation Study located in Annex 2 of this protocol, the term "Clinical Review Form" (CRF) should be understood to refer to either a paper form or an electronic data record or both, depending on the data collection method used in this study.

A CRF is required and should be completed for each included patient in the Validation Study. The completed original CRFs are the sole property of Pfizer and should not be made available in any form to third parties, except for authorized representatives of Pfizer or appropriate regulatory authorities, without written permission from Pfizer. The investigator shall ensure that the CRFs are securely stored at the study site in encrypted electronic and/or paper form and will be password protected or secured in a locked room to prevent access by unauthorized third parties.

The third party responsible for performing medical record review has ultimate responsibility for the collection and reporting of all clinical, safety, and laboratory data entered on the CRFs and any other data collection forms (source documents) and ensuring that they are accurate, authentic/original, attributable, complete, consistent, legible, timely (contemporaneous), enduring, and available when required. The CRFs must be signed by the third party responsible for performing medical record review or by an authorized staff member to attest that the data contained on the CRFs are true. Any corrections to entries made in the CRFs or source documents must be dated, initialed, and explained (if necessary) and should not obscure the original entry.

The source documents are the hospital or the physician's chart. In these cases, data collected on the CRFs must match those charts.

#### 9.6.4. Record Retention

To enable evaluations and/or inspections/audits from regulatory authorities or Pfizer, HealthCore and IQVIA agree to keep all study-related records, including the identity of all participating patients (sufficient information to link records, e.g., CRFs and hospital records copies of all CRFs, safety reporting forms, source documents, detailed records of treatment disposition, and adequate documentation of relevant correspondence (e.g., letters, meeting minutes, and telephone call reports). The records should be retained by the third party responsible for performing medical record review, according to local regulations or as specified in the vendor contract or research agreement, whichever is longer. The third party responsible for performing medical record review, must ensure that the records continue to be stored securely for so long as they are retained.

If the third party responsible for performing medical record review becomes unable for any reason to continue to retain study records for the required period (e.g., retirement, relocation), Pfizer should be prospectively notified. The study records must be transferred to a designee acceptable to Pfizer such as another investigator, another institution, or to an independent third party arranged by Pfizer.

Study records must be kept for a minimum of 15 years after completion or discontinuation of the study, unless third party responsible for performing medical record review and Pfizer have expressly agreed to a different period of retention via a separate written agreement. Record must be retained for longer than 15 years or as required by applicable local regulations.

